7.5 SECONDARY ENDPOINT(S)

7.5.1 Key secondary endpoint(s)

This section is not applicable as no key secondary endpoint has been specified in the protocol.

7.5.2 (Other) Secondary endpoint(s)

The analyses for the secondary endpoints as described in Section 5.2.2 will be mainly based on frequency counts and percentages along with 95% CIs.

Means and standard deviations will be displayed for the endpoint on cerebral venous recanalisation as measured by the change in number of occluded cerebral veins and sinuses after up to 24 weeks. Patients with missing or not analyzable MRI scans at EOT will be excluded from this analysis.

The frequency of patients with new intracranial haemorrhage ("ICH") or worsening of the haemorrhagic component of a previous lesion will be presented, along with 95% CIs. The single components of this composite endpoint will be presented in the same way.

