### **2.2 TRIAL OBJECTIVES**

This is an exploratory trial to investigate the efficacy and safety of dabigatran etexilate versus dose-adjusted warfarin in patients with CVT after initial acute treatment.

The primary objective is to compare the net clinical benefit of the treatment arms, as measured by the composite of VTE (recurring CVT; DVT of any limb, PE, or splanchnic vein thrombosis) + major bleeding according to ISTH criteria after up to 24 weeks.

Secondary objectives include a comparison of additional efficacy and safety parameters.

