## **7. STATISTICAL METHODS AND DETERMINATION OF SAMPLE SIZE**

### **7.1 STATISTICAL DESIGN - MODEL**

This study is a PROBE (Prospective, Randomised, Open label, Blinded Endpoint), multicentre, international, parallel group study with an active control and equal treatment allocation. This phase III study is planned to investigate the efficacy and safety of dabigatran etexilate versus dose-adjusted warfarin in patients with CVT over a 24-week period. The primary endpoint is a composite of the number of patients with new VTE (CVT, DVT, PE, splanchnic vein thrombosis) or major bleeding according to ISTH criteria after up to 24 weeks.

The study is an exploratory trial and not intended for registration. No formal statistical hypothesis will be tested. All analyses are descriptive in nature and confidence intervals and p-values from statistical models are used for exploratory purposes only.

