### 7.3.2 Secondary endpoint analyses

Secondary analyses will be based on the FAS for the following endpoints: number of patients with CVT, DVT, PE, splanchnic vein thrombosis and the endpoint on cerebral venous recanalisation as measured by the change in number of occluded cerebral veins and sinuses after up to 24 weeks.

The following analyses will be based on the treated set: number of patients with major bleeding according to ISTH, number of patients with clinically relevant non-major bleeding, as well as the composite of the two mentioned above, number of patients with any bleeding, number of patients with composite endpoint of new ICH or worsening of the haemorrhagic component of a previous lesion.

The analyses for the secondary endpoints as described in Section [5.1.2](#) will be mainly based on frequency counts and percentages along with 95% confidence intervals.

Means and standard deviations will be displayed by treatment arm for the endpoint on cerebral venous recanalisation as measured by the change in number of occluded cerebral

veins and sinuses after up to 24 weeks. Means and standard deviations will be displayed by stratification factor of presence or absence of ICH at baseline. Patients with missing or not analysable MRI scans at EOT would need to be excluded from this analysis.

The composite endpoint of new ICH or worsening of the haemorrhagic component of a previous lesion will be categorized as described in Section [5.3.5.1](#). This ordinal endpoint will be analysed with Cochrane-Mantel-Haenszel test.

Further specification of analyses can be found in the TSAP.

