4. CHANGES IN THE PLANNED ANALYSIS OF THE STUDY

In the CTP version 1 only three analysis populations have been defined: treated set (TS), full analysis set (FAS) and per protocol set (PPS). A screened set (SCR) as described in CTP version 2 (01FEB2017) will also be created for display of disposition tables, etc., see Section 6.3.

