 - Cerebellar veins will be scored as system, irrespective of the number of occluded veins (i.e. 0 points if none is fully occluded; 1 point if at least one is fully occluded)
- 3. For each individual patient a total score will be calculated at baseline and at the EOT.
- 4. A recanalisation score will subsequently be calculated for each patient as the difference between the baseline total score and the EOT total score.

Page 10 of 30

Proprietary confidential information © 2018 Boehringer Ingelheim International GmbH or one or more of its affiliated companies

Table 5.2.2: 1	Categorisation o	f haemorrhagic br	rain lesions (Vo	on Kummer et al [13])
----------------	------------------	-------------------	------------------	-----------------------

Class	Туре	Description
1	Haemorr	hagic transformation of infarcted brain tissue
1a	HI-1*	Scattered small petechiae, no mass effect
1b	HI-2	Confluent petechiae, no mass effect
1c	PH-1*	Haematoma within infarcted tissue, occupying <30%, no substantive mass effect
2	Intracerebral haemorrhage within and beyond infarcted brain tissue	
	PH-2	Haematoma occupying 30% or more of the infarcted tissue, with obvious mass effect
3	Intracerebral haemorrhage outside the infarcted brain tissue or intracranial-extracerebral haemorrhage	
3a	Parenchymal haematoma remote from infarcted brain tissue	
3b	Intraventricular haemorrhage	
3c	Subarachnoid haemorrhage	
3d	Subdural haemorrhage	

* HI: haemorrhagic infarction; PH: parenchymatous haematoma

Any new haemorrhagic brain lesion will be categorised as Class 3 (Intracerebral haemorrhage outside the infarcted brain tissue or intracranial-extracerebral haemorrhage). If there is more than one haemorrhagic lesion present on imaging, the category of the most severe lesion is assigned.

For each patient, intracranial haemorrhage will be classified at baseline and EOT (in case there is no EOT visit, the classification based on the last on-treatment images up to 6 days after last study drug intake will be taken for the determination of worsening).

Worsening is defined as follows:

- Class 3 is worse than class 2, which is worse than class 1.
- Within class 1, type PH-1 (1c) is worse than type HI-2 (1b), which is worse than type HI-1 (1a).
- Within class 3 (a, b, c, d), an increase of at least 25% in volume is considered a worsening.

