7. PLANNED ANALYSIS

Patient disposition (number of patients screened, randomised, treated, discontinued, etc...) will be presented for all patients.

Disposition as well as demographic and baseline data will be displayed by treatment group and overall. Primary, secondary and further as well as safety endpoints will be displayed by treatment group.

Descriptive statistics for continuous variables will generally be N (number of patients with non-missing values), mean, standard deviation (SD), minimum, Q1 (lower quartile), median, Q3 (upper quartile), maximum. In general, means, medians, Q1 and Q3 will be presented to one more decimal place than the raw data and SDs will be presented to two more decimal places. Minima and maxima will be presented to the same number of decimal places as the raw data.

Tabulations of frequencies for categorical data will include all possible categories and will display the number of observations in a category as well as the percentage relative to the respective treatment group. Percentages will be rounded to one decimal place. A missing category will be displayed if and only if there are actually missing values. Percentages will be based on all patients in the respective patient set whether they have non-missing values or not.

For calculations, 7 days will be considered 1 week, 30 days will be considered 1 month.

Generally, displays will follow [1], [3] and [6].

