7.4 PRIMARY ENDPOINT(S)

This is a prospective, randomised, open label, blinded endpoint (PROBE), active comparator trial and the clinical endpoints are being adjudicated by an AC in a blinded fashion. All analyses are exploratory, no statistical hypothesis will be tested.

The number and frequency of patients by treatment as well as by subgroup will be displayed along with the 95% confidence intervals (CIs). No difference between the treatments dabigatran etexilate versus warfarin will be tested.

Hazard ratios (HR) and 95% CI will be calculated as well; however the result will only be considered interpretable if the CI is not too wide, i.e. (lower limit of CI) \geq (estimate of HR / 4) and (upper limit of CI) \leq (4 * estimate of HR). A Cox proportional hazard model stratified by ICH at baseline will be applied.

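### Recanalisation is only summarised by arm: no between-arm difference with CI is planned, and no adjustment for the baseline occlusion score that caps the change

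*SAP*

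**What the plan says.** SAP 5.2.2 scores each vein or sinus item 1 for full occlusion and 0 for partial or no occlusion, sums the items, and defines the recanalisation score as "the difference between the baseline total score and the EOT total score". For its analysis, SAP 7.5.2 says: "Means and standard deviations will be displayed for the endpoint on cerebral venous recanalisation". Patients without an analysable EOT MRI are left out. SAP 7 adds that "Primary, secondary and further as well as safety endpoints will be displayed by treatment group" and lists the statistics for continuous variables: N, mean, SD, quartiles and range. The 95% CIs in SAP 7.5.2 belong to frequency counts and percentages.

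Three other statements bear on this:

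- Protocol 2.2: "Secondary objectives include a comparison of additional efficacy and safety parameters".
- Protocol 7.1: "confidence intervals and p-values from statistical models are used for exploratory purposes only".
- SAP 7.4, for the primary endpoint: "A Cox proportional hazard model stratified by ICH at baseline will be applied".

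Protocol 7.3.2 also plans one breakdown for recanalisation: "Means and standard deviations will be displayed by stratification factor of presence or absence of ICH at baseline". The visible SAP 7.5.2 does not repeat it. SAP 4 does not list it as a change; the only item there is the screened set, which "will also be created for display of disposition tables".

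**The concern.** The change score depends strongly on where a patient starts. Someone with one fully occluded segment can gain at most 1. Someone with only partial occlusions scores 0 and cannot improve. Randomisation is stratified by ICH alone (Protocol 7.6), so the baseline score is left to chance.

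From N, mean and SD by arm a reader can derive an unadjusted difference and its interval, but not a baseline-adjusted one. Chance imbalance is not a bias, and the unadjusted standard error allows for it. In the one trial that is run, however, an imbalance moves the displayed difference between arms, and the change-score summaries do not separate it from a treatment difference.

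This matters more here because the primary comparison will rest on very few events. The other secondary efficacy endpoint, VTE, is a component of the same composite. Among the visible primary and secondary endpoints, recanalisation is the only efficacy measure that gives a graded value for every patient with analysable scans.

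**Working it through.** **Inputs from the documents.** Protocol 7.7: 60 per arm, 10% drop-out, primary event rate 2-3%. SAP 5.2.2: scoring items. Protocol 1.1: recanalisation in 40-90% of patients. That figure is per patient; it is used below only as a rough range for the chance that one segment reopens.

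**Assumed, because the documents give no value.** SDs, the baseline-EOT correlation, the distribution of the baseline score, and the within-patient correlation of reopening.

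1. **The plan's own figure.** 120 × 0.90 = 108 and 60 × 0.90 = 54 per arm. Reproduced.

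2. **The cap.** 5 items scored singly + 6 grouped = 11, each 0 or 1. Change = baseline − EOT with EOT ≥ 0, so the largest possible gain equals the baseline score.

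3. **Information in the primary endpoint.** Expected events: 120 × 0.02 = 2.4 to 120 × 0.03 = 3.6. SAP 7.4 treats the hazard ratio as interpretable only if both CI limits lie within a factor of 4 of it: 1.96 × SE ≤ ln 4 = 1.386, so SE² ≤ 0.50. With SE² ≈ 1/d₁ + 1/d₂, at least 8 events are needed (4 and 4). The binomial chance of 8 or more among 120 is 0.3% at a 2% rate and 2.9% at 3%.

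4. **Unadjusted precision.** 95% CI half-width = t(0.975, 106) × SD × √(2/54) = 0.38 × SD of change.

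5. **Gain from adjustment, general formula.** With k = SD(EOT)/SD(baseline) and r the baseline-EOT correlation, the variance ratio of ANCOVA to raw change is k²(1 − r²)/(1 + k² − 2rk), and the CI narrows by 1 − √ratio.

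| k | r = 0 | r = 0.4 | r = 0.8 | CI narrower by |
|---|---|---|---|---|
| 0.75 | 0.36 | 0.49 | 0.56 | 25-40% |
| 1 | 0.50 | 0.70 | 0.90 | 5-29% |
| 1.25 | 0.61 | 0.84 | 1.00 | 0-22% |

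6. **Gain, model that respects the cap.** Given baseline B, let the change be beta-binomial with reopening probability p and within-patient correlation ρ. Then E(change | B) = pB, and the ratio is (1 − p)M/[(1 − p)M + p·Var(B)], where M = E(B) + ρ[E(B²) − E(B)]. Three assumed baseline distributions were used (mean/SD 1.95/1.07, 2.09/1.62, 1.40/0.80), with ρ from 0 to 0.6.
   - Lowest ratio at p = 0.4 (2.09/1.62, ρ = 0): 0.6 × 2.09/(0.6 × 2.09 + 0.4 × 2.62) = 0.54.
   - Highest ratio at p = 0.4 (1.40/0.80, ρ = 0.6): M = 1.40 + 0.6 × 1.20 = 2.12, giving 0.6 × 2.12/(0.6 × 2.12 + 0.4 × 0.64) = 0.83.

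| p | Ratio | CI narrower by |
|---|---|---|
| 0.4 | 0.54-0.83 | 9-26% |
| 0.65 | 0.30-0.64 | 20-45% |
| 0.9 | 0.08-0.27 | 48-72% |

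   Half-widths are 0.25-0.61 segments raw and 0.13-0.41 adjusted.

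7. **Chance imbalance.** One trial in 20 has a baseline difference beyond 1.96 × SD × √(2/54): 0.30 segments for SD 0.8 and 0.60 for SD 1.6. Multiplied by p, the raw difference moves by 0.302 × 0.4 = 0.12 to 0.604 × 0.9 = 0.54 segments.

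8. **Validity of the adjusted interval.** In simulations with 54 per arm and no treatment effect (18 settings, 1,500 trials each), the ANCOVA interval with HC3 robust SE covered 93.7-96.1%. A further check with and without a treatment effect gave 94-95%.

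**The case against.** **The plan is openly descriptive.** It tests no hypothesis, its sample size has no statistical basis, and no secondary endpoint has a named between-arm difference. A display by arm can be called a comparison, and Protocol 7.1 permits model-based intervals without promising any. This is fair, and it keeps the point from being an error in the plan. It does not argue against an exploratory estimate with a CI, which tests nothing.

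**The Cox model is a weak precedent.** By SAP 7.4's own rule its result will probably be set aside, and it stratifies only by the randomisation factor. True, but that makes the recanalisation comparison more important.

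**Some SAP text is not visible.** SAP 5.3 (further endpoints), for example, is cited but cannot be seen. A further recanalisation analysis, or tables of baseline and EOT scores by arm, may exist. The finding is therefore limited to the visible text.

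**The size depends on assumptions.** The count model in step 6 ignores new occlusions and reading differences, although baseline may be CT or DSA and EOT must be MRI with MR venography (Protocol 5.2.6). Suppose each unoccluded segment reads as occluded at EOT with an assumed probability q = 0.05, and ρ = 0. The residual variance becomes E(B)p(1 − p) + (11 − E(B))q(1 − q) and the explained variance (p + q)²Var(B). For mean/SD 1.40/0.80 at p = 0.9 the ratio is 0.582/(0.582 + 0.578) = 0.50, a gain of 29%. For 1.95/1.07 it is 0.605/(0.605 + 1.033) = 0.37, a gain of 39%. At p = 0.4 the gains are 7% and 11%. This trims the top of the range but leaves a gain. The 0.54-segment shift also pairs the largest SD with the largest p.

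**Conclusion.** The point holds for the visible text. Recanalisation is to be described by arm, with no contrast, no interval for one, and no use of the baseline score that bounds the outcome. This is a gap in precision and reporting, not a bias or a wrong figure.

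Its size cannot be fixed from the documents. Adjustment could narrow the interval hardly at all (EOT more variable than baseline and highly correlated with it) or by well over a third (high reopening rates, wide spread at baseline). Gains above about 50% need p near 0.9 and few new or misread occlusions. Confidence in the size is medium. The cap itself is arithmetic.

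Whether the by-ICH display of Protocol 7.3.2 is still planned is a point to confirm. Its absence from SAP 7.5.2 does not show that it was dropped.

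**What to change.** In SAP 7.5.2:

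- Add one exploratory ANCOVA of the EOT total score (or the change) on treatment, baseline total score and ICH randomisation stratum, in FAS patients with analysable scans.
- Report the adjusted mean difference with a 95% CI, using a robust SE because the score is a bounded count whose variance depends on baseline.
- Keep the planned means and SDs by arm.
- Report, per arm, how many patients have a baseline score of 0, since the model adds no information on improvement for them.
- State that the by-ICH display of Protocol 7.3.2 is kept, or list its removal in SAP 4.

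The ICH term adds little precision; it is included to match the stratified randomisation. The cost is SAP wording and one model on variables already collected. The downside is a linearity assumption for a bounded count, which did little harm to coverage in the simulations. The model should be specified before database lock: the trial is open-label, and a model chosen after the data are seen by arm would be less credible.

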7.7 EXTENT OF EXPOSURE

The date of first administration is recorded at visit 2.

Days on treatment = date of last administration - date of first administration + 1 day

There will be one summary of duration of exposure [weeks] including treatment interruptions (i.e. they will not be substracted from days on treatment), and one excluding treatment interruptions (i.e. they will be substracted from days on treatment).

Duration of exposure class [weeks]: ≤ 8 weeks (56 days), >8 weeks (56 days) to ≤ 16 weeks (112 days), >16 weeks (112 days) to ≤ 24 weeks (168 days), >24 weeks (168 days)

Additionally, time to permanent discontinuation of trial medication will be analyzed.

7.8 SAFETY ANALYSIS

7.8.1 Adverse events

Adverse events (AEs) will be coded with the most recent version of MedDRA.

Unless otherwise specified, the analyses of AEs will be descriptive in nature. All analyses of AEs will be based on the number of patients with AEs and NOT on the number of AEs.

For analysis of AE attributes such as duration, severity, etc. multiple AE occurrence data on the CRF will be collapsed into AE episodes provided that all of the following applies:

- The same MedDRA lowest level term was reported for the occurrences
- The occurrences were time-overlapping or time-adjacent (time-adjacency of 2 occurrences is given if the second occurrence started on the same day or on the day after the end of the first occurrence)
- Treatment did not change between the onset of the occurrences OR treatment changed between the onset of the occurrences, but no deterioration was observed for the later occurrence

For further details on summarization of AE data, please refer to [5], [7].

The analysis of AEs will be based on the concept of treatment emergent AEs. That means that all AEs occurring between first drug intake till 6 days after last drug intake will be assigned to the randomised treatment. For details on the treatment definition, see Section 6.1.

According to ICH E3 [8], AEs classified as 'other significant' needs to be reported and will include those non-serious and non-significant adverse events with

(i) 'action taken = discontinuation' or 'action taken = reduced', or

(ii) marked haematological and other lab abnormalities or lead to significant concomitant therapy as identified by the Clinical Monitor/Investigator at a Medical and Quality Review Meeting.

Boehringer Ingelheim Page 26 of 30 Proprietary confidential information © 2018 Boehringer Ingelheim International GmbH or one or more of its affiliated companies

An overall summary of AEs will be presented.

The frequency of patients with AEs will be summarised by treatment, primary system organ class (SOC) and preferred term (PT). Separate tables will be provided for patients with serious AEs, AEs leading to treatment discontinuation, AEs leading to death, other significant AEs according to ICH E3 and AEs considered to be drug-related by the investigator (any, as well as serious). Furthermore, AEs will be summarised by intensity. For data disclosure purposes, non-serious AEs will also be provided in separate tables.

The system organ classes will be sorted according to the standard sort order specified by the European Medicines Agency (EMA), preferred terms will be sorted by descending frequency (within SOC).

The overall summary, as well as the frequency table of patients with any AEs by SOC and PT, will also be presented by stratification factor intracranial haemorrhage ("ICH") at baseline as assessed by investigator.

For the listings AEs will be presented per the period in which they occurred, for details see Section 6.1.

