### **7.3 PLANNED ANALYSES**

The following analysis sets will be defined for this trial:

- **Screened Set (SCR):**  
All patients who sign informed consent and complete at least some screening procedures.
- **Treated set:**  
The set includes patients who receive at least one dose of study medication and will be analysed according to the treatment they have received.
- **Full analysis set (FAS):**  
All patients randomised will be analysed in the treatment group to which they are randomised regardless of whether they took study medication. The start date of the observation period for this analysis set is the date of randomisation. This follows the intent-to-treat (ITT) principle.
- **Per protocol set (PPS):**  
This is a subset of the Treated set, restricted to patients without important protocol violations. Important protocol violations will be defined in the TSAP. If the number of patients excluded from PPS is small, (e.g. <10% of the Treated set), then analyses on this set may not be conducted.

The efficacy analysis based on FAS will follow the ITT principle. Patients will be allocated to the randomised treatment groups regardless of actual medication taken.

Two observation periods are defined:

- Full observation period: from date of randomisation until the end of the trial, including all observed time on and off trial medication until the last known alive date (or date of death).
- On-treatment: from date of first intake of trial medication until discontinuation of trial medication + 6 days.

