#### **7.3.4 Safety analyses**

AEs will be coded using the Medical Dictionary for Drug Regulatory Activities (MedDRA) coding dictionary available at database lock. Standard BI summary tables and listings will be produced. All AEs with an onset between start of trial medication and end of the REP, a period of 6 days after the last dose of trial medication, will be assigned to the treatment period for evaluation.

All treated patients will be included in the safety analysis. In general, safety analyses will be descriptive in nature and will be based on BI standards. No hypothesis testing is planned.

Statistical analysis and reporting of AEs will concentrate on treatment-emergent AEs. To this end, all AEs occurring between start of treatment and end of the residual effect period will be considered 'treatment-emergent'. The residual effect period is defined as 6 days. AEs that start before first drug intake and deteriorate under treatment will also be considered as 'treatment-emergent'.

Frequency, severity, and causal relationship of AEs will be tabulated by system organ class and preferred term after coding according to the current version of MedDRA.

Laboratory data will be analysed both quantitatively as well as qualitatively. The latter will be done via comparison of laboratory data to their reference ranges. Values outside the reference range as well as values defined as clinically relevant will be highlighted in the listings. Treatment groups will be compared descriptively with regard to distribution parameters as well as with regard to frequency and percentage of patients with abnormal values or clinically relevant abnormal values.

Vital signs, physical examinations, or other safety-relevant data observed at screening, baseline, during the course of the trial and at the end-of-trial evaluation will be assessed with regard to possible changes compared to findings before start of treatment.

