6. GENERAL ANALYSIS DEFINITIONS

6.1 **TREATMENT(S)**

The following treatment periods based on actual start and stop dates/times of randomised study drug administration are defined:

- Screening: date of informed consent (time "0:00:00") to date of randomisation (time "0:01:00")
- Post-randomisation: date of randomisation (time "0:01:00") to time-point of first intake (date and time, "0:02:00" if time is missing) of randomised study drug.
- On-treatment: first intake (date and time)/date restarted of randomised study drug to date stopped/last intake (date and time) of randomised study drug. The residual effect period (REP) of 6 days will be added to this period.
- Off-treatment: date randomised study drug stopped + REP to date randomised study drug restarted
- Post-treatment: last intake (date/time) of randomised study drug + REP until date of trial completion. This is the date given on the termination page (trial completion page) of the eCRF. If date of trial completion is before last intake + REP, REP will be cut accordingly.
- Post-study: day after date of trial completion to database lock (DBL) + 1 day (time "0:00:00").

The REP is the time period after the last administration of trial medication when measurable drug levels or pharmacodynamic effects are still likely to be present. Events occurring in the REP are handled as occurring on-treatment. Data from the post-study period will only be listed.

For the analysis two observation periods are defined:

- Full observation period: from date of randomisation until the end of the trial, including all observed time on and off trial medication until the last known alive date (or date of death) This observation period will be used for the efficacy analysis.
- On-treatment: from date of first intake of trial medication until discontinuation of trial medication + REP

This observation period will be used for the safety analysis.

Despite the trial being open label, all activities conducted by the trial team will be performed in a blinded manner (as much as possible) until DBL. For example, data tabulations and listings will be presented using dummy treatment group information instead of actual treatment group allocations. The planned data review will be handled by the DMC in an unblinded manner (refer to the DMC SAP for more information).

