6.3 PATIENT SETS ANALYSED

The following analysis sets will be defined for this trial:

- Screened set (SCR) All patients who signed informed consent; these patients will have completed routine procedures to establish the diagnosis of CVT.
- Treated set (TS): The set includes patients who received at least one dose of study medication.
- Full analysis set (FAS): This set includes all patients randomised.
- Per protocol set (PPS): This is a subset of the TS, restricted to patients without relevant important protocol violations as defined in Table 6.2: 1.

Proprietary confidential information © 2018 Boehringer Ingelheim International GmbH or one or more of its affiliated companies

The efficacy analysis (i.e. analysis of primary and secondary efficacy endpoints, as well as further endpoints based on the FAS will follow the intent-to-treat (ITT) principle. Patients will be allocated to the randomised treatment groups regardless of actual medication taken.

The safety analysis (including analysis of secondary safety endpoints

as well as adverse event analysis) will be based on the TS, and patients will be analyzed according to the treatment they have received.

Secondary efficacy analysis on the PPS may not be conducted if the number of patients excluded from the patient set is small (i.e. <10% of the TS).

Disposition data on the SCR will be presented according to the randomized treatment groups. For patients not entered/randomised on the total number will be presented.

			· · , ,	
		Pa	itient set	
Class of endpoint/data	SCR	TS	FAS	PPS
Primary endpoint (Section 5.1)			primary analysis	secondary analysis
Secondary and further efficacy endpoints (Section 5.2.2 and 5.3)			X	
Safety endpoints (Section 7.8)		Х		
Demographic/baseline data (Section 7.1)		Х	(X)	
Disposition	Х			

Table 6.3: 1Patient sets analyzed

(X) An additional FAS presentation of the demographic/baseline data may be provided in the End of Text section of the clinical trial report (CTR) if patient numbers for FAS and TS are clearly different, i.e. if $\geq 10\%$ of the TS are excluded from the FAS.

Note that the number of patients with available data for an endpoint may differ. For details, see Section 6.6 "Handling of missing data and outliers".

Proprietary confidential information © 2018 Boehringer Ingelheim International GmbH or one or more of its affiliated companies

Page 19 of 30

6.5 **POOLING OF CENTRES**

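### SAP 7.8.1 assigns adverse events to the randomised treatment, against SAP 6.3 and Protocol 7.3, and omits the protocol's clause on events that start before the first dose and worsen on drug

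*SAP*

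**What the plan says.** **Who an AE is counted under.** SAP 7.8.1 (Adverse events) states that "all AEs occurring between first drug intake till 6 days after last drug intake will be assigned to the randomised treatment" and refers to SAP 6.1 for the treatment definition. SAP 6.3 places the safety analysis, with AE analysis named as part of it, on the Treated set and says "patients will be analyzed according to the treatment they have received". Protocol 7.3 defines the Treated set in the same way: "The set includes patients who receive at least one dose of study medication and will be analysed according to the treatment they have received".

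**Which periods apply.** SAP 6.1 has two sets of definitions. The first is a list of treatment periods, "based on actual start and stop dates/times of randomised study drug administration". The second defines two observation periods. Its on-treatment period runs from first intake of trial medication to discontinuation plus the residual effect period, and SAP 6.1 says that this one is used for the safety analysis.

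**Which AEs are treatment-emergent.** Protocol 7.3.4 counts AEs from start of treatment to the end of the 6-day residual effect period. It then adds a second group: "AEs that start before first drug intake and deteriorate under treatment will also be considered as" treatment-emergent. SAP 7.8.1 gives the window from first intake to 6 days after last intake and stops there.

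**Declared changes.** SAP section 4 lists only the addition of the Screened Set.

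**The concern.** A programmer who builds the AE tables from SAP 7.8.1 and one who builds them from SAP 6.3 would put a cross-treated patient in different columns. SAP 6.3 also puts the secondary safety endpoints on treatment received. If 7.8.1 were followed to the letter, that patient could appear under one drug in the AE tables and under the other in the bleeding tables of the same report. The SAP foresees such patients: important protocol violation C1 covers cross-treatment and removes them from the Per Protocol Set only, so they stay in the Treated set.

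The omitted clause matters because Protocol 5.3.7 collects AEs from consent, so an event can begin before the first dose and become worse after it. Under the protocol that event is treatment-emergent. Under the SAP definition taken alone, its onset lies outside the window.

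**Working it through.** No planned figure is in dispute, so the check compares the texts, with one illustration of size.

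**Step 1: attribution.**

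| Place | Rule |
|---|---|
| Protocol 7.3, Treated set | treatment received |
| SAP 6.3, safety analysis including AEs | treatment received |
| SAP 7.8.1, AEs in the window | randomised treatment |
| Protocol 7.3.4 | silent; events in the window "will be assigned to the treatment period for evaluation" |

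The conflict is therefore between SAP 7.8.1 on one side and SAP 6.3 and Protocol 7.3 on the other. Protocol 7.3.4 does not bear on attribution.

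**Step 2: treatment-emergent definition.**

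| Element | Protocol 7.3.4 | SAP 7.8.1 |
|---|---|---|
| Onset from first intake to 6 days after last intake | included | included |
| Onset before first intake, worse on treatment | included | not mentioned |

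**Step 3: how far the rest of the SAP fills the gap.** The AE-collapsing rule in SAP 7.8.1 merges occurrences across a change of treatment only where "treatment changed between the onset of the occurrences, but no deterioration was observed for the later occurrence". A worsening that was entered as its own occurrence after first intake would stay separate and fall inside the window. The rule is written for AE attributes such as duration and severity, and it cannot help where the site left the worsening under the AE already recorded. That residue is what the protocol clause would catch.

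**Step 4: size of the attribution point.** The documents give no cross-treatment rate, so the inputs here are assumptions, apart from the planned 60 per arm (Protocol 7.7). Suppose all 60 per arm are treated. Six dabigatran-randomised patients have a given AE, and so do six warfarin-randomised patients who took warfarin. In addition, k patients randomised to warfarin took dabigatran, and each had the AE.

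- As randomised: difference (dabigatran minus warfarin) = 6/60 - (6 + k)/60.
- As received: difference = (6 + k)/(60 + k) - 6/(60 - k).

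| k | Share of 120 | As randomised | Difference (points) | As received | Difference (points) |
|---|---|---|---|---|---|
| 0 | 0% | 10.0% v 10.0% | 0 | 10.0% v 10.0% | 0 |
| 1 | 0.8% | 10.0% v 11.7% | -1.7 | 11.5% v 10.2% | +1.3 |
| 2 | 1.7% | 10.0% v 13.3% | -3.3 | 12.9% v 10.3% | +2.6 |
| 3 | 2.5% | 10.0% v 15.0% | -5.0 | 14.3% v 10.5% | +3.8 |

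The set-up is deliberately unfavourable: every crossing is in one direction and every cross-treated patient has the event.

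**Step 5: size of the deterioration point.** It cannot be calculated. It depends on how many AEs start between consent and first dose, and on how sites record worsening. Neither is stated.

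**The case against.** The best reply on attribution is that the sentence in SAP 7.8.1 is about timing. It points to SAP 6.1, so the phrase about randomised treatment may be only a label for the on-treatment period, with SAP 6.3 governing the columns. That reading is possible. It still leaves two sections with different words for the same rule, so the wording needs to be reconciled. Cross-treatment may also never happen: the trial is open-label, and capsules in bottles are hard to confuse with colour-labelled warfarin tablets. That stands as a limit on size.

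A reader might go further and infer from the treatment-period list in SAP 6.1 that a cross-treated patient has no on-treatment time and that the events are lost. The documents do not support this. The observation period that SAP 6.1 assigns to safety starts with trial medication, not with the randomised drug.

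On the omitted clause, the SAP says that it is based on Protocol section 7 and assumes familiarity with the protocol, so the clause may be meant to carry over. Protocol 5.3.7 requires worsening of the underlying disease or of pre-existing conditions to be recorded as an AE. SAP 7.8.1 also sends further detail to company standards that cannot be seen here, and its listings show AEs by period. It would therefore be too strong to say that the SAP drops these events, since no sentence excludes them. What stands is that its own definition is narrower than the protocol's and no change is declared.

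A reader might also infer that the omission falls unevenly on the arms, because some dabigatran patients wait for a vitamin K antagonist to wash out. Protocol 4.1.4 does make some dabigatran starts later, but it delays some warfarin starts too. With no rates given, an uneven effect is not shown.

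**Conclusion.** The point holds as an inconsistency of wording with a narrow effect. SAP 7.8.1 conflicts with SAP 6.3 and Protocol 7.3 on the treatment under which AEs are counted, and it leaves out the Protocol 7.3.4 clause on pre-dose AEs that deteriorate. SAP 4 declares neither. Followed literally, 7.8.1 would count a cross-treated patient's AEs under a drug that the patient did not take. The consequence is nil without cross-treatment. Under the assumptions shown, it is a shift of about 3 percentage points in one AE comparison for a single such patient (from -1.7 to +1.3). For the omitted clause, only AEs with onset between consent and first dose, and with no new entry for the worsening, are at issue. The primary analysis is unaffected: it uses the Full Analysis Set as randomised over the full observation period.

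**What to change.** 1. In SAP 7.8.1, replace randomised treatment with treatment received, to match SAP 6.3 and Protocol 7.3.
2. In the same section, restore the Protocol 7.3.4 sentence on AEs that begin before first intake and deteriorate under treatment. If it was removed on purpose, list the removal and the reason in SAP section 4.
3. In SAP 6.1, align the treatment-period list, now tied to the randomised study drug, with the on-treatment observation period already defined there by trial medication and used for safety.

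The cost is a few wording changes in the SAP, with no new data. The efficacy analyses do not change.
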